4.3.7. Other Assessments of Disease Response

The proportion of subjects with $\geq 35\%$ reduction in spleen size from baseline and $\geq 50\%$ reduction in score from baseline will be summarized over time. The proportion of subjects with an anemia response for MF patients and with erythroid response for CMML patients will also be summarized over time.

For patients who were transfusion-dependent at baseline, the number and percentage of patients who achieved transfusion independence following treatment start will be summarized for any 12-week period (at any time, at C4D21-12 weeks and C7D28-24 weeks). Transfusion dependency will be for pRBCs, platelets, and both, as defined in [Section 1.2.5.1](#). The rate of transfusions will also be summarized at any time post-baseline, from pre-baseline to baseline, from baseline to Week 12, and from Week 12 to Week 24.

For patients who were Red Blood Cell Transfusion Independent at Baseline, the number and percentage of patients becoming transfusion dependent following treatment start will be summarized for any 12-week period (at any time, at C4D21-12 weeks and C7D28-24 weeks). Transfusion dependency will be summarized pRBC as defined in Section 1.2.5.1.

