1.1.3.2. Stage 2 Study Objectives

The secondary objectives for the study from Protocol Amendment 6 and earlier are to characterize the anti-tumor activity (including response rates, components of the response criteria, duration of response [DOR], progression-free survival [PFS], and overall survival [OS]), pharmacokinetic (PK), and immunogenicity of tagraxofusp.

An additional primary objective of Stage 2 is a preliminary assessment of response rates associated with SL-401 in each of the evaluated MPNs.

Specific components of the International Working Group Myeloproliferative Neoplasms Research and Treatment (IWG-MRT) consensus response criteria and additional clinical parameters for CMML will be assessed as secondary endpoints, including:

- Change in body weight (individual and median) over time.
- Change in hemoglobin (individual and median) over time.
- Change in Eastern Cooperative Oncology Group Performance Status (ECOG PS) (individual and median) over time.
- PFS (as defined in IWG-MRT consensus).
- OS.

Specific components of the IWG-MRT/ European LeukemiaNet consensus response criteria and additional clinical parameters for MF will be assessed as secondary endpoints, including but not limited to:

- Proportion of patients with reduction of $\geq 35\%$ in spleen volume at week 24 (postbaseline, as measured by magnetic resonance imaging [MRI] or computed tomography [CT]).
- Proportion of patients with reduction of $\geq 35\%$ in spleen volume at week 48 (postbaseline, as measured by MRI or CT).
- Proportion of patients (transfusion-dependent at baseline) who achieve transfusion independence (during any 12-week period following initiation of study therapy, as defined in IWG-MRT consensus).
- Proportion of patients who report a reduction in total symptom score of $\geq 50\%$ from baseline to week 24 (as assessed via the Myeloproliferative Neoplasm Symptom Assessment Form Total Symptom Score [MPN-SAF TSS]).
- Change in hemoglobin (individual and median) over time.
- Change in body weight (individual and median) over time.
- Change in ECOG PS (individual and median) over time.
- PFS (as defined in IWG-MRT/ELN consensus).

- OS.

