1.2.5. Efficacy, Pharmacokinetic, and Safety Parameters

1.2.5.1. Efficacy Parameters and Endpoints

Efficacy data from Stages 1 and 2 among patients treated at 12 ug/kg/day will be analyzed with descriptive statistical methods. Further details on the definitions and analysis methods for efficacy endpoints are provided in [Section 4.3](#). Refer to [Section 8](#) for detailed response criteria established for CMML and MF.

Primary Efficacy Endpoint:

The primary efficacy endpoint is investigator assessed objective response rate (ORR) for both CMML and MF. Objective response rate is defined as the number and percentage of patients who achieve disease-specific complete response (CR) or partial response (PR) after treatment.

Time to objective response and bridge to stem cell transplant after objective response will be assessed to support the primary efficacy endpoint.

Specific components of the IWG-MRT/ELN response criteria for defining clinical improvement for MF patients include anemia, spleen, and symptom responses. Specific components of the IWG-MRT response criteria for clinical benefit for CMML patients include erythroid, platelet, neutrophil, spleen, and symptom responses. The datapoints corresponding to each individual component of the responses will also separately be assessed and compared to baseline results for both MF and CMML patients as secondary endpoints. These include spleen volume, transfusion dependency, tumor symptoms score, blast results, absolute monocyte count results, white blood cell count results, hemoglobin results, and platelet results.

MF patients will be classified as “dependent” or “independent” at baseline for packed red blood cells (pRBC) if they received transfusions of at least 6 units in the 12 weeks prior to the study enrollment, for a hemoglobin level of < 85 g/L, in the absence of bleeding or treatment-induced anemia. In addition, the most recent transfusion episode must have occurred in the 28 days prior to study enrollment. Transfusion independence for MF will be defined as patients who experience at least a 12 week period during any point on treatment with no transfusion of that type required, including hemoglobin level of >=85 g/L.

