CMML patients will be classified as “dependent” or “independent” at baseline within each category of platelets, packed red blood cells (pRBC), and both (i.e., receiving both platelets and pRBC) if they received transfusions of at least 4 units in the 8 weeks prior to the study enrollment. Transfusion independence for CMML will be defined as patients who experience at least a 8 week period during any point on treatment with no transfusion of that type required.

Secondary Efficacy Endpoints

The secondary efficacy endpoints are DOR, PFS, OS, and duration of follow-up.

Duration of objective response is defined as the time from when criteria are first met for CR or PR until the date that the criteria for relapse is met. Progression-free survival is defined as the time from the date of first infusion of tagraxofusp to the date of PD or death from any cause. Overall survival is defined as the time from the date of first infusion of tagraxofusp to the date of death from any cause.

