It is underscored that the consensus definition of a CR bone marrow is to be used only in those patients in which all other criteria are met, including resolution of leukoerythroblastosis. It should also be noted that it was a particularly difficult task for the working group to reach a consensus regarding what represents a complete histologic remission.

- 3 Immature myeloid cells constitute blasts + promyelocytes + myelocytes + metamyelocytes + nucleated red blood cells. In splenectomized patients, < 5% immature myeloid cells is allowed.
- 4 See above for definitions of anemia response, spleen response, and progressive disease. Increase in the severity of anemia constitutes the occurrence of new transfusion dependency or a ≥ 20 g/L decrease in hemoglobin level from pretreatment baseline that lasts for at least 12 weeks. Increase in severity of thrombocytopenia or neutropenia is defined as a 2-grade decline, from pretreatment baseline, in platelet count or absolute neutrophil count, according to the CTCAE version 4.03. In addition, assignment to CI requires a minimum platelet count of $\geq 25 \times 10^9$ /L and absolute neutrophil count of $\geq 0.5 \times 10^9$ /L.
- 5 Applicable only to patients with baseline hemoglobin of < 100 g/L. In patients not meeting the strict criteria for transfusion dependency at the time of study enrollment (see as follows), but have received transfusions within the previous month, the pretransfusion hemoglobin level should be used as the baseline.
- 6 Transfusion dependency before study enrollment is defined as transfusions of at least 6 units of pRBCs in the 12 weeks prior to study enrollment, for a hemoglobin level of < 85 g/L, in the absence of bleeding or treatment-induced anemia. In addition, the most recent transfusion episode must have occurred in the 28 days prior to study enrollment. Response in transfusion-dependent patients requires absence of any pRBC transfusions during any consecutive “rolling” 12-week interval during the treatment phase, capped by a hemoglobin level of ≥ 85 g/L.
- 7 In splenectomized patients, palpable hepatomegaly is substituted with the same measurement strategy.
- 8 Spleen or liver responses must be confirmed by imaging studies where a $\geq 35\%$ reduction in spleen volume, as assessed by MRI or CT, is required. Furthermore, a $\geq 35\%$ volume reduction in the spleen or liver, by MRI or CT, constitutes a response regardless of what is reported with physical examination.

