- Normalization of peripheral counts and hepatosplenomegaly with bone marrow blasts (and blast equivalents) reduced by 50%, but remaining > 5% of cellularity except in cases of MDS/MPN with $\leq 5\%$ bone marrow blasts at baseline

Marrow response

- Optimal marrow response: Presence of all marrow criteria necessary for CR without normalization of peripheral blood indices as presented above
- Partial marrow response: Bone marrow blasts (and blast equivalents) reduced by 50%, but remaining > 5% of cellularity, or reduction in grading of reticulin fibrosis from baseline on at least 2 bone marrow evaluations spaced at least 2 months apart

Clinical benefit

Requires 1 of the following in the absence of progression or CR/partial response and independent of marrow response (response must be verified at ≥ 8 weeks) to be considered a clinical benefit. (Note: “Cord blood response” was corrected to “response”.)

- Erythroid response
 - Hgb increase by ≥ 2.0 g/dL
 - Transfusion independence for ≥ 8 weeks for patients requiring at least 4 packed red blood cell transfusions in the previous 8 weeks
 - Only red blood cell transfusions given based on physician’s judgement for a pretreatment Hgb of ≤ 8.5 g/dL will count in the red blood cell TI response evaluation⁵
- Platelet response
 - Transfusion independence when previously requiring platelet transfusions of at least a rate of 4 platelet transfusions in the previous 8 weeks
 - Pretreatment $\leq 20 \times 10^9/L$: increase from $< 20 \times 10^9/L$ to $> 20 \times 10^9/L$ and by at least 100%
 - Pretreatment $> 20 \times 10^9/L$ but $\leq 100 \times 10^9/L$: absolute increase of $\geq 30 \times 10^9/L$ ⁵
- Neutrophil response
 - Pretreatment $\leq 0.5 \times 10^9/L$, at least 100% increase and an absolute increase $\geq 0.5 \times 10^9/L$
 - Pretreatment, $> 0.5 \times 10^9/L$ and $\leq 1.0 \times 10^9/L$, at least 50% increase and an absolute increase $\geq 0.5 \times 10^9/L$ ⁵
- Spleen response
 - Either a minimum 50% reduction in palpable splenomegaly of a spleen that is at least 10 cm at baseline or a spleen that is palpable at more than 5 cm at baseline becomes not palpable

Symptom response (improvement in symptoms as noted by decrease of $\geq 50\%$ as per the MPN-SAF TSSscoring < 20 were not considered eligible for measuring clinical benefit)⁶

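### SAP 4.3.7 gives one 12-week period for transfusion independence, while SAP 1.2.5.1 sets 8 weeks for CMML and 12 for MF; 4.3.7 does not say which applies to CMML

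*SAP*

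**What the plan says.** SAP 1.2.5.1 gives each disease its own rule. For MF: "Transfusion independence for MF will be defined as patients who experience at least a 12 week period during any point on treatment". For CMML: "Transfusion independence for CMML will be defined as patients who experience at least a 8 week period during any point on treatment". In both cases no transfusion of that type may be required during the period, and MF adds a hemoglobin condition. For CMML red cells, Table 8-4 in SAP 8.2 agrees with 1.2.5.1: it asks for independence over at least 8 "weeks for patients requiring at least 4 packed red blood cell transfusions in the previous 8 weeks".

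SAP 4.3.7 then describes the table. For patients dependent at baseline, "the number and percentage of patients who achieved transfusion independence following treatment start will be summarized for any 12-week period", reported at any time, at C4D21 (12 weeks) and at C7D28 (24 weeks). The next sentence says "Transfusion dependency will be for pRBCs, platelets, and both", with a cross-reference to 1.2.5.1. A further paragraph covers patients who were red-cell independent at baseline: "the number and percentage of patients becoming transfusion dependent following treatment start will be summarized for any 12-week period", with the same three reporting labels.

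The 12-week phrase closely matches an MF secondary endpoint in SAP 1.1.3.2, the proportion "who achieve transfusion independence (during any 12-week period following initiation of study therapy, as defined in IWG-MRT consensus". The CMML list in that section has no transfusion item.

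**The concern.** The transfusion paragraph of 4.3.7 covers CMML. The paragraph before it names CMML erythroid response, and the platelet and combined categories it uses are defined in 1.2.5.1 for CMML only. A CMML table will therefore be produced under a sentence that states 12 weeks, although the CMML definition elsewhere in the SAP is 8 weeks.

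The cross-reference does not settle this. It is attached to dependency by product, while the sentence on independence states its own period. Two programmers could reasonably produce different CMML counts.

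What is at stake is the coherence of the study report. A CMML patient could meet the 8-week red-cell criterion, and so be an erythroid responder in the 4.3.1 table, yet appear in the 4.3.7 table as never having become independent.

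**Working it through.** **The plan's own figure.** SAP 3.1.2 and Protocol 14.2.2 give 80% probability of at least one responder among 10 patients at a true rate of 0.15. This reproduces: 1 − 0.85^10 = 0.803. It is not in dispute.

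**Two readings of the 12-week phrase in 4.3.7.**

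| Reading | Support in the SAP | Consequence for CMML |
|---|---|---|
| Required transfusion-free duration | Near-identical wording of the MF endpoint in 1.1.3.2, where 12 weeks is the duration; Table 8-1 footnote 6 ("Response in transfusion-dependent patients requires absence of any pRBC transfusions during any consecutive" rolling 12-week interval); the any-time row has no fixed reporting end | 8 to <12 weeks counts under 1.2.5.1 but not in the table |
| Observation window | The C4D21 and C7D28 labels; transfusion rates given for baseline to Week 12 and Week 12 to Week 24; the same phrase used for patients becoming dependent, where it cannot mean a transfusion-free duration | 4.3.7 does not state the qualifying duration |

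**Calendar (nominal, no cycle delays).** C4D21 = 4 × 21 = 84 days = week 12. C7D28 = 84 + 3 × 28 = 168 days = week 24.

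- By week 12, a 12-week rule needs no transfusion at all since first dose (latest start of the free period 12 − 12 = week 0). An 8-week rule allows a start as late as 12 − 8 = week 4.
- By week 24, the latest starts are 24 − 12 = week 12 and 24 − 8 = week 16.
- Two episodes split 168 days into three gaps, so the longest is at least 168/3 = 56 days and the 8-week rule is always met. Episodes on days 56 and 112 leave no 84-day gap.

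**Illustration under the required-duration reading only.** Assume n episodes fall uniformly at random over T weeks (my assumption; the documents give no timing). With x = w/T for a w-week rule, the probability that the longest gap is at least w weeks is Σ over k ≥ 1 of (−1)^(k+1) · C(n+1, k) · (1 − kx)^n, keeping only terms with 1 − kx > 0.

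| T (weeks) | n | 8-week rule | 12-week rule |
|---|---|---|---|
| 12 | 1 | 2 × (1/3) = 67% | 0% |
| 24 | 2 | 3 × (2/3)^2 − 3 × (1/3)^2 = 100% | 3 × (1/2)^2 = 75% |
| 24 | 3 | 4 × (2/3)^3 − 6 × (1/3)^3 = 96% | 4 × (1/2)^3 = 50% |
| 24 | 4 | 5 × (2/3)^4 − 10 × (1/3)^4 = 86% | 5 × (1/2)^4 = 31% |

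With a constant-rate Poisson process over 24 weeks (also assumed), the pairs are 99% vs 88% at 0.05 episodes per week, 60% vs 20% at 0.25, and 16% vs 2% at 0.5.

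**Weight of one patient.** Protocol 14.2.2 planned about 8 to 10 dependent patients per cohort, so one patient is 1/8 = 12.5 or 1/10 = 10.0 points. Clopper-Pearson 95% intervals: 1/8 (0.3–52.7%) against 0/8 (0–36.9%); 1/10 (0.3–44.5%) against 0/10 (0–30.8%).

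**Dependence definitions for CMML.**

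- SAP 1.2.5.1: at least 4 units in the 8 weeks before enrollment.
- SAP 3.1.2 and Protocol 14.2.2: at least 4 transfusions in the 8 weeks before first dose. Table 8-4 also counts transfusions in its response criteria.
- Table 8-4, progression footnote 4: at least 2 red-cell units in the past month for hemoglobin below 8.5 g/dL, without overt bleeding. This is an on-study rule.

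The first two can give different denominators for the conversion table. The third differs from the 1.2.5.1 rule to which 4.3.7 points for new dependence.

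**The case against.** The best defence is that 4.3.7 describes reporting windows, within which the 8-week CMML rule of 1.2.5.1 applies, so no patient is lost. The reuse of the phrase for patients becoming dependent is good evidence for this. It stands to this extent: a reader might infer that CMML responders will be undercounted, and the text does not establish that. The loss follows only under the required-duration reading. The defence does not remove the gap, because 4.3.7 still states no CMML duration.

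A reader might also infer that MF and CMML patients are pooled. They are not: SAP 3.5 and 4.3 present efficacy separately by disease. That separates the display but leaves the period the same.

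A third tempting inference is that this undermines the Stage 3A activity decision, since conversion to independence is one of its two outcomes. The documents do not support it. SAP 5 records that Stage 3A enrollment was not continued and Stage 3B not started, that the remaining analyses are descriptive, and that further transfusion analyses were added without pre-specification. Nothing states that the 4.3.7 table implements the Stage 3A outcome. The activity rule also accepted either outcome, so losing one transfusion converter need not have changed it.

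Finally, 8-week results survive elsewhere: erythroid and platelet responses in 4.3.1, their durations in 4.3.2, and by-patient listings. This limits the harm. However, those response categories also accept count rises, so they do not isolate conversion. The table shells are in a separate document (SAP 9) and may state the rule; that cannot be checked here.

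**Conclusion.** SAP 4.3.7 is wrong as written, with minor severity and moderate confidence. Its single 12-week period conflicts with the 8-week CMML definition if it is a required duration, and leaves the CMML duration unstated if it is an observation window. Only under the first reading is the direction certain: the CMML count falls or stays the same. MF is unaffected, because 12 weeks matches its definition.

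The size is unknown. The percentages in the tables rest on assumed episode timing. The 10.0 to 12.5 points per patient rests on planned subset sizes that may not have been reached. The harm is a possible internal inconsistency in the CMML results of the study report, with no effect on a go/no-go decision.

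**What to change.** In SAP 4.3.7:

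- Count independence as at least 8 consecutive transfusion-free weeks for CMML and at least 12 for MF, per 1.2.5.1.
- State that C4D21 (week 12) and C7D28 (week 24) are reporting time points, and give the interval in which the qualifying period must fall, for example treatment start to that time point.
- State one observation period for the any-time row, since 1.2.5.1 refers to time on treatment and 4.3.7 to time after treatment start.
- In the new-dependence paragraph, state which on-study CMML rule applies, reconciling 1.2.5.1 (a baseline classification) with progression footnote 4 of Table 8-4.

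Secondarily, in 1.2.5.1, reconcile the CMML baseline wording (units before enrollment) with SAP 3.1.2 and Protocol 14.2.2 (transfusions before first dose).

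The cost is a few sentences and some table programming, with no new data. The drawback is that an 8-week gap is easier to reach by chance (16% against 2% over 24 weeks at 0.5 episodes per week, under the Poisson assumption). A 12-week CMML count can therefore be kept as a labelled sensitivity row.

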4.3.8. Laboratory Efficacy Results

4.3.8.1. Bone Marrow Blasts

Bone marrow blasts will be summarized over time for all patients. In case of different methods used to assess bone marrow at the same visit (i.e aspirate and biopsy) but only one method was used at baseline, the method used at baseline will be considered for comparison. In case both methods are used in all visits, the larger blast results between biopsy results and aspirate results for a subject will be presented. In case only one method is used in a specific visit, it will be considered regardless the method used at baseline.

The number and percentage of patients with $\geq 50\%$ reduction in bone marrow blasts from baseline and the number and percentage of patients with $< 5\%$ blasts will be summarized at any time for CMML patients with baseline blasts $\geq 5\%$.

The maximum percent reduction from baseline and the maximum increase from baseline across all post-baseline visits will be summarized for CMML patients. A waterfall plot of the maximum percent reduction in blasts, blasts at Cycle 4 Day 21 visit, and blasts at Cycle 7 Day 28 will be created.

Mean and standard error will be plotted over time for CMML.

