- 2 The end-of-cycle evaluations (Day 21 or thereafter) may also serve as the pre-infusion evaluations for the subsequent cycles; with the exception of vital signs, these assessments do not need to be duplicated on successive days unless there is an abnormality or other clinically relevant reason for repeat evaluation.
- 3 Refer to protocol [Section 16.3](#) (Patient Information and Informed Consent) and [Section 7](#) (Populations to be Studied) for details.
- 4 Urine or serum pregnancy test must be performed within 1 week prior to treatment for WOCBP.
- 5 Height will be measured at screening only; weight does not need to be measured more than once per day, and should be measured pre-infusion on treatment days. Vital signs should be performed after patient is sitting for 3 to 5 minutes. During dosing period, vital signs should be taken immediately prior to infusion, at 0 (i.e., immediately after completion of infusion), and at 30 and 60 minutes post-infusion.
- 6 A MUGA scan or 2-D ECHO to quantify LVEF must be completed within 28 days prior to start of first cycle of study drug.
- 7 To be collected prior to tagraxofusp infusion if during dosing period. Hematology includes WBC count with differential, RBC count, hematocrit, Hb, platelet count, and immature myeloid cells (including blasts + myelocytes + promyelocytes + nucleated red blood cells) (for safety assessments as well as efficacy assessments at the end of each cycle in between bone marrow assessments).
- 8 To be collected prior to tagraxofusp infusion if during dosing period. Serum chemistry includes electrolytes and additional parameters (equivalent to Chem-20): ALT, albumin, ALP, AST, bilirubin, BUN, calcium, chloride, creatinine, glucose, LDH, phosphate, potassium, sodium, total protein, uric acid, and CPK. See Appendix [Section 18.3](#) for administration of albumin if serum albumin decreases to < 3.0 g/dL (< 30 g/L) during treatment days or in the immediate post-treatment period.
- 9 In lieu of PT, INR may be measured.
- 10 Morphology and WBC differential/blast count on aspirate. Baseline must be performed within 28 days prior to the first administration of tagraxofusp. Subsequent bone marrow aspirates and biopsies will be performed at the end of C1 and C4 and then every 12 weeks (±7 days) thereafter. Bone marrow evaluation should also be performed at

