End of Treatment including patients who discontinue study therapy prior to completion of C4; if a bone marrow evaluation was performed within 4 weeks prior to the end of treatment, a repeat evaluation does not need to be performed at this time, unless clinically indicated.

- 11 Bone marrow aspirate and imaging studies are to be repeated at the end of C1 and C4 and then every 12 weeks (± 7 days) thereafter.
- 12 A baseline MRI or CT scan must be performed within 28 days prior to the first administration of tagraxofusp. Subsequent imaging studies will be performed at the end of C1 and C4 and then every 12 weeks (± 7 days) until there is evidence of relapsed or progressive disease. Abdominal scan is required; evaluation of chest/pelvis may be obtained at the Investigator's discretion. Scan must include measurement of spleen and liver volume. Subsequent to Week 24, for patients receiving ongoing therapy (or those who discontinue therapy but are without evidence of PD and continue to be evaluated in ongoing follow-up) the frequency of imaging studies may be reduced (obtained less frequently) if peripheral blood and/or clinical assessments indicate clinical stability, as per the Investigator's discretion, in consultation with the Medical Monitor. Imaging should also be performed at End of Treatment, including patients who discontinue study therapy prior to completion of C4; if a imaging was performed within 4 weeks prior to the end of treatment, a repeat evaluation does not need to be performed at this time, unless clinically indicated. Whenever clinically feasible, it is strongly requested that the same imaging modality (MRI or CT) at both baseline and subsequent timepoints be utilized for any given patient throughout their evaluation on-study.
- 13 Peripheral blood (serum) samples (10 mL) will be collected for the detection of tagraxofusp reactive antibodies on Day 1 (pre-infusion) and Day 21 (the end of cycle collection may also serve as the pre-infusion collection for the subsequent cycle).
- 14 Premedications administered 60 minutes (± 15 minutes) before tagraxofusp treatment: Diphenhydramine 50 mg IV (or an equivalent dose of another H₁-histamine antagonist); acetaminophen 650 mg orally (or equivalent dose of paracetamol); methylprednisolone 50 mg IV (or an equivalent dose of another corticosteroid); famotidine 20 mg IV (or an equivalent dose of another H₂-histamine antagonist).

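### SAP 4.3.8.1 lets marrow-blast change compare biopsy with aspirate, and sets no baseline when both methods were done at baseline but only one later

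*SAP*

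**What the plan says.** SAP 4.3.8.1 (Bone Marrow Blasts) has three rules for choosing between aspirate and biopsy.

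1. If a visit has both methods "but only one method was used at baseline, the method used at baseline will be considered for comparison".
2. "In case both methods are used in all visits, the larger blast results between biopsy results and aspirate results for a subject will be presented".
3. "In case only one method is used in a specific visit, it will be considered regardless the method used at baseline".

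The section then defines the outputs. The numbers with a reduction of at least 50% and with blasts below 5% "will be summarized at any time for CMML patients with baseline blasts" of 5% or more. "The maximum percent reduction from baseline and the maximum increase from baseline across all post-baseline visits will be summarized for CMML patients". A waterfall plot and a plot of means over time are also planned.

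SAP 3.4 defines baseline as the latest pre-dose measurement and does not choose between methods. In the protocol, Table 4 note 10 specifies "Morphology and WBC differential/blast count on aspirate" and schedules both aspirates and biopsies at repeat visits. Note 11 of the same table mentions only the aspirate: "Bone marrow aspirate and imaging studies are to be repeated at the end of C1 and C4".

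**The concern.** Rule 1 protects a like-with-like comparison and rule 3 abandons it. A patient with an aspirate at baseline and only a biopsy later gets a percent change that mixes a method difference with any real change. Section 4.3.8.1 provides no flag and no sensitivity summary for such a value.

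There is also a gap. Suppose both methods were done at baseline and only one at a later visit. Rule 3 fixes the later value. Rule 1 does not apply, because baseline had two methods. Rule 2 does not apply, because it needs both methods at all visits. Nothing fixes the baseline value. A programmer might well take the larger reading, by analogy with rule 2, and that would tilt the comparison towards reduction.

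This pattern is foreseeable. Note 11 of protocol Table 4 names only the aspirate for repeats, and footnote 2 to the Stage 3A response criteria (protocol Table 8, SAP Table 8-4) waives a second biopsy for proving resolution of fibrosis when the first showed none of significance.

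At stake are efficacy displays in a small, uncontrolled study. With about 20 patients planned per Stage 3A cohort, one misclassified patient moves a percentage by 1/20 = 5 points, and by more in the subset with baseline blasts of at least 5%.

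**Working it through.** The documents give no figure for this rule and no reading error for marrow blasts, so there is no plan figure to reproduce.

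**Examples without any error model.** Both carry the larger baseline reading into the mixed case.
- Aspirate is 4% at both visits and biopsy is 6% at baseline only. The patient enters the subset through the 6% and is then counted as below 5% through the 4%. The aspirate never changed.
- Baseline aspirate is 5% and biopsy 10%; the later aspirate is 5%. Change = (5 − 10)/10 = −50%, a counted reduction. Aspirate against aspirate gives 0%.

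Readings this close to 5% are expected, since eligible CMML-1 includes marrow blasts of 5–9% (protocol 7.1.1, criterion 10).

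**Model.** Assume no true change and independent lognormal readings with coefficient of variation CV, so the log-scale SD is s = √ln(1 + CV²). At CV 30%, s = √ln 1.09 = 0.294.

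*Like-with-like, single readings.* P(ratio ≤ 0.5) = Φ(−ln 2 / (s√2)) = Φ(−0.693/0.415) = Φ(−1.67) ≈ 4.8%. The median change is 0%.

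*Larger-of-two baseline, one later reading.* The log of the larger of two readings exceeds the log of a single one by s/√π on average = 0.294 × 0.564 = 0.166. The geometric-mean change is therefore exp(−0.166) − 1 ≈ −15%. The false-reduction rates come from simulation (400,000 patients). The three-visit column counts a reduction at any of three visits, all of them mixed in the last two columns.

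| CV | Like-with-like, one visit | Three visits | Larger baseline vs one reading, one visit | Three visits |
|---|---|---|---|---|
| 20% | 0.7% | 1.8% | 1.3% | 3.4% |
| 30% | 4.8% | 11.3% | 8.3% | 19.4% |
| 40% | 10.2% | 22.2% | 17.1% | 35.6% |
| 50% | 15.0% | 30.7% | 24.2% | 47.3% |

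*Larger of two at both time points (rule 2 as written).* At CV 30% the one-visit rate is 2.2%, below the 4.8% for single readings.

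*Method switch.* Let the later method read q times the baseline method. Then P = Φ((−ln 2 − ln q)/(s√2)). At CV 30%:

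| q | Median change | False reduction of at least 50% |
|---|---|---|
| 0.7 | −30% | 21.0% |
| 0.8 | −20% | 12.9% |
| 1 | 0% | 4.8% |
| 1.25 | +25% | 1.3% |
| 1.43 | +43% | 0.6% |

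If switches at q = 0.7 and q = 1.43 were equally common, the average would be (20.95 + 0.56)/2 ≈ 10.8%, still above 4.8%.

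*Both effects together.* Let one method read 0.7 times the other, with the larger baseline and CV 30%. The rate is 22.9% if the lower-reading method is the one repeated, but 5.0% if the higher-reading one is. The size therefore depends on which method is repeated.

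**The case against.** A reader might infer that the section manufactures blast reductions and so favours the drug. The documents do not support that. The larger-of-two rule is written only for patients with both methods at every visit, where it treats baseline and follow-up alike. Its use in the mixed case is an inference about an undefined situation. A method switch has no fixed direction either: if the later method reads higher, false reductions fall below the like-with-like rate and real ones may be hidden.

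A reader might also want rule 2 deleted. That is not supported. Applied at both time points it gives fewer false reductions than single readings (2.2% against 4.8%), and it is strict for the count below 5%, because the larger reading must be below 5%.

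The case for leaving the text alone rests on reach. The primary endpoint is investigator-assessed ORR (SAP 1.2.5.1), which does not use these rules. The blast summaries are descriptive and were added in SAP Version 2.0. Type I error is not controlled (SAP 3.7). Stage 3A enrolment was stopped and Stage 3B will not start (SAP section 5). By-patient listings are planned. Protocol Table 4 note 10, Table 5 note 7 and section 11.12.2 schedule both methods at each marrow time point, so mixed visits may be few. All of this stands and limits the consequence. It does not remove a stated rule that permits a cross-method change, or supply the missing baseline.

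**Conclusion.** The point holds in a limited form. Rule 3 expressly permits a biopsy-versus-aspirate change from baseline, contrary to the principle of rule 1, and the baseline is undefined when both methods were done at baseline and one later. The direction of error from a switch is unknown. Overstatement of reductions is conditional on the larger baseline being used: about 8% against 5% per visit and 19% against 11% over three visits at 30% CV, with no true change and all three visits mixed.

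The CV, the method ratio and the three visits are assumptions, and the table above shows how far the rates move between 20% and 50% CV. The documents do not say how often methods will differ between visits, so no cohort-level effect can be stated. The affected outputs are the counts of at least 50% reduction and of blasts below 5%, the maximum-reduction summary and the waterfall plot.

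**What to change.** Amend SAP 4.3.8.1 as follows.

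- Replace rule 3: compare each post-baseline value with the baseline value from the same method. When both methods were done at baseline and one later, use the baseline reading from the method repeated. The protocol schedule places the blast count on the aspirate, so this should normally be the aspirate.
- Keep the larger-of-two rule, but only where both methods exist at baseline and at the visit being compared.
- State which method sets the subset with baseline blasts of at least 5%. This needs its own sentence, because the baseline used for percent change may now differ between visits within a patient.
- Treat a visit with no same-method baseline as not evaluable for percent change, and say how it counts. Under SAP 3.10 percentages use the total population including missing results, so a patient with only such visits would stay in the denominator as a non-responder unless the text says otherwise.

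The cost is SAP wording and programming. The downside is that some visits lose a percent-change value.
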